June 2017	Registered on www.clinicaltrials.gov
August 2017	Recruitment and training of field interviewers
September – October 2017	Baseline survey and intervention
September – November 2017	Job search workshops, HIV testing vouchers
November – December 2017	Follow-up survey, home-based HIV testing

December 2017	Updated on www.clinicaltrials.gov
January – August 2018	Data extraction, quality checks, passive follow-up of HIV testing in the AHRI surveillance
September 17, 2018	Final Protocol and Pre-Analysis Plan posted to www.clinicaltrials.gov
September 18, 2018	Randomization status unblinded to researchers and posted to www.clinicaltrials.gov
March 2018 – January 2019	Analysis and preparation of manuscripts

A13. Funding and Registration

This randomized trial was jointly funded by two grants from the National Institutes of Health: 1K01MH105320 ([name]) “Economic, health, and behavioral dimensions of HIV treatment scale-up” and 1R01HD084233 ([name]/[name]) “Causal pathways to population health impact of HIV antiretroviral treatment”.

The trial is registered on www.clinicaltrials.gov as NCT03215901.

* * *

B. PRE-ANALYSIS PLAN

B1. Outcomes Variables and Definitions

B1.1 Primary Outcome Measures

Behaviors

1. Participation in HIV testing

Definition: Use of HIV testing voucher to be provided OR participation in HIV testing during surveillance household survey visit conducted at 1 to 2 months follow-up.

[Time Frame: 2 months]

2. Composite measure of future-oriented behaviors

Definition: Count variable (range 0:3) equal to the sum of the following indicators:

- Participation in HIV testing (either via the voucher or home-based testing)
- Attendance at a job search skills workshop: 1=attended
- Allocation of funds to savings tin during baseline interview: 1=participant allocated at least 50 Rand (out of 100 Rand) to the savings tin

Beliefs and Attitudes

3. Change in subjective life expectancy (at 2 months)

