Definition: Participants will be offered the opportunity to test for HIV via a household visit by the AHRI surveillance team 4-6 weeks after the baseline survey. By linking with the AHRI surveillance, we will assess whether individuals tested in the AHRI home visit. All those who tested will be coded as 1; all others, including those who were not at home will be coded as 0.

[Time Frame: 1 month]

Use of clinical HIV services

Definition: For individuals who are HIV-infected, the intervention could increase linkage to care and retention on HIV treatment. We will assess use of clinical HIV services as a binary indicator for whether the individual sought care in the public sector HIV care and treatment program in the three months after baseline. Clinical data from the public sector HIV treatment program are routinely linked into the population surveillance platform by AHRI data management.

[Time Frame: 3 months]

Self-reported behaviors

Change in time allocated to education or labor supply

Definition: At both baseline (pre-intervention) and 2-months follow-up, we ask respondents to report hours spent on different activities in the last week. These questions were adapted from the Malawi Living Standards Measurement Survey, Module E (p17). We will assess change in the total hours spent on the following activities (aggregating time spent across these activities):

- a household business
- formal work for pay
- informal work for pay
- apprenticeship/internship
- looking for work
- schooling
- job training

(The activities that we measured but excluded from this list are: housework, caregiving, socializing with friends, doing nothing, and sleep)

[Time Frame: 2 months]

Change in self-reported savings

Definition: Difference between baseline and 2-month follow up in response to the following question: how much have you saved in bank accounts, at home, or elsewhere?

[Time Frame: 2 months]

Change in self-reported non-HIV health risk behaviors

Definition: We will assess changes between baseline and 2-month follow-up in self-reported health risk behaviors. We will conduct statistical testing on an additive index of the following: any smoking in the last week; any drinking in the last week; any heavy drinking (3+ drinks) in the last week; does not always use a seatbelt. Range of this index will be 0 to 4.

[Time Frame: 2 months]

Change in self-reported unprotected sexual activity

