Definition: We will assess changes between baseline and 2-month follow-up in self-reported unprotected sex. Specifically, we will assess number of times a person reported having condomless sex in the last 30 days.

[Time Frame: 2 months]

Change in self-reported current HIV care-seeking

Definition: We will assess change between baseline and 2-month follow-up in a combined self-report measure of whether the respondent either tested for HIV within the last 3 months and whether the respondent is currently taking ARVs.

[Time Frame: 2 months]

Employment, education, and care-seeking outcomes in the AHRI surveillance

Definition: We will assess longer run education, employment, migration, and care-seeking outcomes observed through household proxy report and clinic linkage in the AHRI population-based surveillance platform. Specifically, we will assess whether the respondent is reported to be in school, working, looking for work, or none of the above; whether the respondent is still residing in the surveillance area; and whether the respondent has linked to clinical HIV services.

[Time Frame: 1 year, 2 years]

Attitudes and beliefs

Change in beliefs about life expectancy in the community

Definition: at baseline and at 2-month follow-up, we ask people to consider 20 people their age and gender in the community and to estimate how many they think will be alive at age 30, 40, ... 80. We will construct a measure of perceived community life expectancy by linearly interpolating the responses to these questions (starting at the respondent's age) and computing the area under the curve. This value is the average number of years they expect a demographically similar person in the community to live.

[Time Frame: 2 months]

Change in beliefs about lifetime risk of HIV infection

Definition: change between baseline and 2-month follow-up in the subjective probability (out of 20) of becoming HIV-infected at some point in their life. Although we do not expect that the video will change underlying beliefs about HIV risk; it could change people's willingness to consider these risks, which would be important to know in interpreting our results.

[Time Frame: 2 months]

Change in beliefs about work and schooling

Definition: At baseline and 2-month follow-up we asked respondents about the chances (out of 20) that they would complete different levels of schooling and about the chances they would be employed in the future. We will assess changes in these beliefs.

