Logistic regression model. We will also estimate our primary models using multivariate logistic regression to assess sensitivity to specification. In lieu of odds ratios, we will report marginal effects associated with the treatment arm, to enable comparison with the estimate from the OLS models. Again, standard errors will be clustered at the household level.

Restrict to HIV-uninfected. HIV testing uptake – one of our primary outcomes – is less relevant for individuals who already know their current HIV status. In a robustness check, we will assess HIV uptake after excluding: individuals who reported that they had ever tested for HIV and were certain that they were HIV positive at baseline (20 out of 20 beans); and individuals who reported testing for

HIV in the prior 3 months and reported that they were sure that they were HIV negative (0 out of 20 beans).

Remove participants with inconsistent answers and extreme outliers. A small number of participants reported inconsistent answers to the survival expectations questions at baseline. We will assess robustness of results after removing: participants who reported non-zero chances of survival at ages greater than the “oldest possible age” they could imagine living to; participants who reported that it was unlikely they would live to 60 years but allocated >10 beans; participants who reported that it was likely they would live to 60 years but allocated <10 beans. Demographic differences between persons with consistent and inconsistent answers will be reported.

B7. Adjusting Inference for Multiple Hypothesis Testing

No adjustments will be made for our primary outcomes.

For secondary outcomes, the primary manner in which we adjust for multiple hypotheses being tested is by grouping outcomes into indices such that their joint significance will be tested. If we do not find that there is overall significance for aggregated measures of behaviors such as local of control, we will not move test statistical significance of individual index components. In addition, for families of outcomes where we are interested in testing the treatment effect both for an index overall as well as individual components, when the number of tests is large (greater than 10), we adjust our standard errors using the Benjamini-Hochberg procedure[24] for controlling the false discovery rate to less than 0.05.

B7. Handling attrition

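### The B6 check labelled as HIV-uninfected does not select uninfected participants, and its 20-bean rule can retain people who already know they are positive

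*Combined protocol and SAP*

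**What the plan says.** Section B6 lists a check labelled "Restrict to HIV-uninfected". Its reason is that testing uptake "is less relevant for individuals who already know their current HIV status". The rule reads: "In a robustness check, we will assess HIV uptake after excluding" two groups:

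- on the positive side, people described as having "ever tested for HIV and were certain that they were HIV positive at baseline (20 out of 20 beans");
- on the negative side, people with a recent test, in the plan's words "HIV in the prior 3 months and reported that they were sure that they were HIV negative (0 out of 20 beans").

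Nothing else enters the rule. Two further sources on known positive status appear elsewhere in the plan:

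- Section B1.2, *Change in self-reported current HIV care-seeking*, uses a self-report of "whether the respondent is currently taking ARVs", measured as a change from baseline.
- Section B1.2, *Use of clinical HIV services*, says: "Clinical data from the public sector HIV treatment program are routinely linked into the population surveillance platform by AHRI data management". Section A11 describes the same linkage, and section A9.0 says that consent covers linkage to the surveillance data.

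The outcome named in the check is testing uptake. The composite (primary outcome 2 in B1.1) also contains "Participation in HIV testing (either via the voucher or home-based testing") as one of three items.

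**The concern.** The label describes infection status, but the rule works on certainty about status. A reader of the results table would take the restricted set to be uninfected people, and it is not.

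Separately, the check exists to show what happens to the testing result once people who already know their status are set aside. It recognises known positives by one survey answer at its extreme value, together with a self-report of ever having tested. A person in HIV care knows their status, yet neither reported ARV use nor a care record affects who is excluded. Anyone who hedges on the bean question, or does not disclose in the interview, can remain in the set meant to exclude them. At stake are the description of the restricted population and how cleanly the check does its job.

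**Working it through.** **1. The rule, enumerated.** The inputs are the two exclusions in B6 and bean counts from 0 to 20 (21 possible values).

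| Reported testing history | Bean counts excluded | Bean counts kept |
|---|---|---|
| Never tested | none | 21 of 21 |
| Ever tested, not in the prior 3 months | 20 | 20 of 21 |
| Tested in the prior 3 months | 0 and 20 | 19 of 21 |

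True infection status, surveillance HIV status and ARV use never change the result.

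**2. Against the label.** Recently tested people who are sure they are negative are removed, although they are likely to be uninfected. An infected person giving 1–19 beans is kept whatever their testing history, and so is an infected person who reports never testing. The set is people not certain of their status.

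**3. Against the stated reason.** Both exclusions remove people who claim to know their status, one on each side, so the rule follows its reason reasonably well. The gap is on the positive side. A participant who reports ARV use, or who has a care record from before baseline, is kept with 19 beans or fewer, or with any count if they report never testing. The one exception is a person who reports a recent test and gives 0 beans, who is removed by the second exclusion.

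**4. Size.** The plan gives no figure for this check, no bean distribution and no share on ARVs at ages 18–25. The one-third HIV prevalence in A3 is for all adults. For scale I take the 10-point difference (10% to 20%) in Example 2 of A7, which refers to the voucher or the workshop rather than to the combined testing outcome.

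First, the plan's own figure, with 225 per group, two-sided 5% (assumed) and no allowance for clustering:

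- null standard error = √(2 × 0.15 × 0.85 / 225) = 0.0337
- alternative standard error = √((0.10 × 0.90 + 0.20 × 0.80) / 225) = 0.0333
- power = Φ((0.10 − 1.96 × 0.0337) / 0.0333) = 0.846

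This is consistent with the claim in A7 that such a difference is detectable.

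Now let d be the share of those kept who already know they are positive and whose testing does not respond to the video. Both the share and the zero response are assumptions. The effect seen in the check is 10 × (1 − d) points:

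- d = 2%: 10 × 0.98 = 9.8 points; power 0.834
- d = 5%: 10 × 0.95 = 9.5 points; power 0.813

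The power figures use 225 per group for comparison only. The restricted sample will be smaller, by an amount that the documents do not give.

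**5. Cost in precision.** Removing a further share d multiplies the standard error by about 1/√(1 − d), which is 1.010 at 2% and 1.026 at 5%.

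**The case against.** The exclusions are written out in full, so any analyst can apply them without ambiguity, and they match their reason on both sides. On this view only the heading is wrong. That stands for the part about the label.

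The ARV case needs someone who takes treatment yet gives fewer than 20 beans or reports never testing. A consistent reporter is already excluded. A reader might infer that ARV users are known to be in the restricted set. The documents do not show this. It is a possibility that the rule leaves open.

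A reader might also infer that B6 is the only place where certainty about status is considered. It is not: the subgroup part of A4 plans to compare the video's effect on testing between more and less certain respondents, although B5 does not list that analysis.

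A third inference is that omitting the composite is an error, because the B6 lead-in speaks of primary outcomes in general. The text does not support that. The lead-in does not promise every check for every outcome, and the reason given here concerns testing only. Workshop attendance and saving, the other two items, are as relevant to people who know their status as to anyone else.

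Finally, a reader might apply a known-status share of 25–50% and conclude that a 10-point effect shrinks to 7.5 or 5 points. That is dilution in the whole sample, from a group that B6 already largely removes for outcome 1, and the share is not in the documents. What matters for this check is the share still left after the exclusions.

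What remains is the untrue label and a gap on the positive side that data already planned for can close.

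**Conclusion.** The point holds in a limited form. The label is wrong on the face of the text. The rule is broadly right for its purpose but identifies known positives too narrowly, given that baseline ARV self-report and linked care records are available.

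The effect on the check is probably small: 0.2–0.5 points off a 10-point difference if 2–5% of those kept are non-responding known positives. That range is assumed, and the true number cannot be computed from the documents.

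A reader might infer that the primary results are compromised. They are not. This is a robustness check defined on pre-video answers, and the primary analyses do not use it.

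**What to change.** - Rename the check *Status not already known at baseline*.
- Keep the two existing exclusions. Also exclude participants who reported current ARV use in the pre-video baseline survey, or who have a linked public-sector HIV care record dated before baseline. The date limit matters because care sought after baseline is itself a secondary outcome in B1.2 and could be affected by the video.
- Report how many participants each criterion removes, by arm.
- Optionally, re-run the composite in this set as a supplementary result, noting that the rationale applies only to its testing item.

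The cost is a few lines of wording and a slightly smaller restricted sample; no new data collection is needed. The timeline in A12 puts unblinding at September 18, 2018, one day after posting of the plan. A change made after that should be dated and labelled as such, with the result under the posted rule shown beside it.

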Appendix A. Sampling Strategy

Appendix B. Consent Form

Appendix C. Randomization Procedures

Appendix A. Sampling Strategy

Sampling Protocol

The sampling frame was all young adults who resided in bounded structures located in PIPSA week blocks 33-41 and were part of the AHRI PIPSA eligibility list. Young adults were defined as individuals who were 18 years or older on August 15, 2017 and were 25 years or younger on October 1, 2017. Week blocks 34-41 were selected because the AHRI surveillance was scheduled to visit these weekblocks for the annual surveillance visit and HIV testing 4 weeks after we would be there. With the AHRI surveillance 2 weeks behind schedule, we are expecting our respondents to be visited by the surveillance 4-6 weeks after the baseline survey visit. The AHRI eligibility list includes those known to reside in the surveillance and includes all those who resided in the surveillance at last visit in 2016 as well as some known to have moved in.

We randomly sampled Bounded Structures within each week block and included all individuals in each Bounded Structure. We proceeded until we had 120 individuals per Week Block, or 20 per field worker per week. We anticipate that each field worker will be able to complete 10-15 interviews per week.

The target sample size for interviews completed was 450. We assumed a 62.5% response rate, which is similar to prior studies of young adults at AHRI. Based on this response rate, we estimated that we needed to sample 720 individuals to complete 450 interviews. With a 6-field worker team and 2.5 interviews conducted per field worker per day, we project that the baseline survey will be completed in six weeks.

We sampled 8 weeks of data to ensure that if unforeseen circumstances (e.g., difficulties locating respondents, fieldworker absences, etc.) dictate lower productivity, then we will have respondents already sampled to finish fieldwork.

Our “stopping rule” for study enrollment is defined as: “Data collection will proceed for six weeks. If at the end of six weeks, we have not yet recruited 450 participants, then data collection will continue for a seventh week. If at the end of seven weeks, we have not yet recruited 450 participants, then data collection will continue for an eighth week. If after eight weeks, we still have not attained 450 participants, we will cease enrollment.”

We have sampled 20 potential respondents per interviewer. Each interviewer is responsible for making three contacts with these respondents during the week. The total number (currently 20) of respondents allocated to each interviewer may change during the pilot stage, depending on what are acceptable workloads.

The following table describes the sampling strategy:

Week Block	Sample Size	Expected Interviews completed	Under the lower productivity scenario
34	120	75	58
35	120	75	58
36	120	75	58
37	120	75	58
38	120	75	58
39	120	75	58
40	120	0	58
41	120	0	50
TOTAL	960	450	450

Appendix C. Randomization Procedures

Variables Randomized. Study participants are randomized with respect to:

- 1) Intervention video vs. no intervention video
- 2) Pure control vs. attention placebo control (among those randomized to no intervention video)
- 3) 20 Rand vs. 5 Rand cost to reserve spot at job search skills workshop
- 4) Male-vs.-female-oriented HIV transmission questions

1. Intervention video vs. no intervention video

Level of randomization. Individuals are randomized to video intervention vs. control. Randomization is at the bounded structure level, so that all respondents within a bounded structure get the same treatment.

Stratification. Randomization is stratified by weekblock to ensure approximately equal numbers of treated and controls within weekblocks.

Constrained (restricted) randomization. The AHRI data contain robust information on baseline covariates. However, because randomization is at the level of the bounded structure, it was not possible to stratify by individual characteristics. Instead, we use a constrained (aka restricted[25]) randomization approach. For the primary analysis – comparison of intervention video vs. no intervention video, we constrained randomization to force balance on the following characteristics: sex, age, whether the person was in school, orphan status, HIV positive status, HIV negative status (unknown is the third category), and household asset quintile. We randomized the intervention treatment assignment (intervention video vs. no intervention video) 3078 times using different randomization seeds. Each time, we assessed balance on key characteristics through a t-test (i.e regression of treatment assignment on the covariate). All randomization seeds that lead to a maximum t-test value greater than 1.68 ($p<0.1$) were excluded. This excluded 62% and retained 38% of the seeds (1060 seeds). We then randomly selected two seeds from these 1060 acceptable seeds. One was used to randomize the video, the other was used to randomized the incentive for the job search skills workshop. We assessed correlation of these two interventions and re-randomized if the Chi2 p-value for the cross-tab was less than 0.5 (see tables below).

2. Pure control vs. attention placebo control (among those randomized to no intervention video)

Within the control group – i.e. individuals assigned to “no intervention video” – we used simple randomization to assign respondents to “pure control” (no video) and to “attention placebo control” (video on another topic).

3. 20 Rand vs. 5 Rand to reserve spot at job search skills workshop

Participants were given 30 or 15 Rand and were then asked to pay 20 or 5 Rand respectively to reserve a spot in the job search skills workshop. Randomization was conducted as described above in concert with the intervention video comparison.

4. Male-vs.-female-oriented HIV transmission questions.

In the survey, respondents were asked to report on the chances that an HIV-negative woman (man) would become HIV-infected after having sex with an HIV-positive man (woman). We used simple randomization to assign respondents to the male-focused or female-focused HIV transmission questions.

Data management procedures

These random treatment assignments – video assignment, job search workshop incentive assignment, together with their AHRI internal ID numbers were submitted to the AHRI data management core, which linked them with the operational data.

Blinding

The investigators are blinded to randomization assignment throughout data collection, cleaning, and development of the analysis plan. Randomization status with respect to the intervention and placebo videos will not be revealed until after all data on the primary outcome (including uptake of testing in the 2017 AHRI surveillance) have been collected, the data have been cleaned, and final pre-analysis plan is posted.[26]

Tables. Intervention video stratified by weekblock and approximately balanced vs. Job Skills Workshop incentive

tab week TreatmentArm				
week	TreatmentArm		Total	
	C	T		
34	60	60	120	
35	60	60	120	
36	60	60	120	
37	61	59	120	
38	60	60	120	
39	60	60	120	
40	59	61	120	
41	62	58	120	
Total	482	478	960	

tab TreatmentArm JobWorkshopArm, chi2				
TreatmentA rm	JobWorkshopArm		Total	
	C	T		
C	245	237	482	
T	243	235	478	
Total	488	472	960	

Pearson chi2(1) = 0.0000 Pr = 0.998
